**Table 5. Potential Interview Topics grounded in Sekhon et al. Theoretical Framework**

	Constructs	Operationalized Topics
Prospective Acceptability: prior to participating in PrEP4Her	Affective Attitude	
 
Feelings about PrEP4Her
 

	Burden	
 
How much effort was required to participate in PrEP4Her
 

	Ethicality	
 
Did PrEP4Her align with your values
 

	Intervention Coherence	
 
How well did you understand PrEP4Her and how it worked
 

	Opportunity Costs	
 
How much values or perceived benefits were given up to engage in PrEP4Her
 

	Perceived Effectiveness	
 
How well did PrEP4Her achieve its purpose
 

	Self-efficacy	
 
Confidence in performing behaviors required to participate in PrEP4Her
 

Note: For Black cis-gender women, questions will be framed around the PrEP4Her implementation strategy that targeted patients.

**Data Analysis.** Drs. [name] and [name] will lead coding and the analytic approach. We will develop a preliminary codebook including *a priori deductive codes*, based on constructs from our theoretical framework, *inductive codes* that emerge from the data and *pattern codes* that connect concepts to one another. The coding team will code a sub-set of transcripts in parallel to compare coding and adjust codebook definitions until adequate inter-coder reliability is achieved.

**Feasibility:** We will measure whether PrEP4Her is appropriate for a larger, full-scale implementation trial by surveying out key-stakeholders prior to interviews (conducted to assess acceptability).

**Procedures.** Feasibility will be measured using the validated scale *Feasibility of Intervention Measure (FIM)* (Cronbach's alpha 0.85-0.91). This includes straightforward items such as "[PrEP4Her] was appealing to me", "[PrEP4Her] seemed suitable", and "[PrEP4Her] seemed easy to implement", which respondents rate on a 5-point Likert scale.

**Statistical Analysis:** Descriptive statistics, using medians and inter-quartile ranges and frequencies, will be calculated to characterize feasibility.

**Fidelity:** We will evaluate the "fidelity" or degree to which our implementation strategy (PrEP4Her) was implemented as designed. Specifically, we have chosen to evaluate components of PrEP4Her that are

measurable and reflect the end-user perspective, including: universal sexual health screening of cis-gender women seen within our GYN pilot site, receipt of educational material about PrEP, communicated with a provider about PrEP. We have selected to evaluate fidelity to measure the effect of type III errors on overall effectiveness of PrEP4Her to increase PrEP uptake and to guide future, large-scale implementation.

**Procedures.** During the 6-month pilot, all patients seen during this period will be given a flyer by staff upon clinic checkout with information to take a brief 5-minute on-line survey, with a compensation of \$20. We will stop recruitment after 300 surveys have been completed. A QR code, website and contact information for study staff will be located on the clinic document. While this intervention is tailored to Black cis-gender women in terms of educational material and tailored communication with providers, implementation strategy components are universal to all patients seen and, therefore, we will not conduct targeted sampling.

**Methods.** Brief electronic surveys will include the following questions: 1) Did your provider (or other clinical staff) take a history asking about your sexual activities and health?, 2) Did you see educational materials during your visit about HIV prevention and a prevention methods call PrEP, 3) Did you speak with a provider about PrEP? AND 4) For those who spoke with a provider about PrEP, would you please describe the conversation and how you felt about communicating with your provider about this prevention strategy?

**Data Management.** REDCap (Research Electronic Data Capture) will be used for electronic surveys and is a secure, Web-based application designed to support data capture for research studies.

**Data Analysis.** Quantitative survey data: Descriptive statistics, using medians and inter-quartile ranges and frequencies to determine fidelity. Qualitative survey data: A similar analytic approach used for data analysis of acceptability will be used, except deductive coding will not be included in analyses.

**Expected Outcomes:** Completion of this aim will provide the necessary information to refine PrEP4Her for broader dissemination in a multi-site implementation study with a step-wedge design.

**C4. Potential Challenges and Alternative Strategies:** (1) Provider uptake of PrEP4Her: It is often challenging to engage clinical care teams to conduct interventions due to workflow demands and time constraints. This may impact the overall efficacy of PrEP4Her due to low adoption and lack of fidelity to PrEP4Her components. To overcome this barrier, investigators will work with leadership in identifying “champions” within the clinic setting to encourage PrEP4Her implementation. Inclusion of a physician practicing in the GYN continuity clinic as a part of our investigative team embeds a committed champion within our pilot site. (2) Recruitment of Black cis-gender women: We plan to recruit Black cis-gender women from our clinical site, to take part in both interviews and quantitative surveys throughout this proposal. We will use well-established research advertising through UAB, but also will leverage provider referral and referral from our research staff to meet recruitment goals. [name] has shown that such networks have been successful in recruiting almost 800 Black cis-gender women for PrEP research studies in AL. (3) Selection bias: we acknowledge the potential for selection bias – Black cis-gender women who are interested in participating in our study may have less HIV and PrEP stigma than the general population. We will make efforts to recruit online and at our clinical site with non-stigmatizing, health promoting messaging to engage a representative sample. (4) Measuring PrEP adherence: due to time and budgetary constraints, we will not evaluate persistence or quantitate adherence with drug levels in the blood or hair, which would be the gold standard to measure adherence to PrEP for those prescribed; however, this is not currently a primary endpoint for this study. In a subsequent efficacy trial, we will measure adherence more definitively.

**C5. Study Timeline:** See study timeline supplement for detailed timeline.

Table 6. PrEP4Her 3-year study timeline	Year 1			Year 2			Year 3		
Aim 1: Focus Groups Black women									
Aim 1: Key-informant Interviews									
Aim 1: Surveys of GYN providers									
Aim 2: Development and Refinement PrEP4Her									
Aim 3: PrEP4Her Intervention									
Manuscript Preparation and Dissemination									

**C6. Impact and Future Directions:** Upon completion of our Aims, we will have developed a culturally tailored strategy to improve uptake of PrEP among Black cis-gender women, ready for further testing. If PrEP4Her shows feasibility, acceptability and preliminary efficacy in enhancing PrEP uptake for Black cis-gender women, we will prepare a subsequent R01 application to conduct a fully powered, implementation science trial across multiple gynecological care sites across the South. Even in the absence of preliminary efficacy of the pilot, the knowledge gained around determinants and components to include in our PrEP4Her implementation strategy to integrate PrEP services into GYN settings will provide novel insights to inform future HIV prevention research among this highly impacted group.

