**Table 4. Specification of Hypothesized Components of Implementation Strategy (“PrEP4Her”)**

[figure not shown]
Named PrEP4Her components	1. Universal sexual health screening for GYN patients 2. Synchronous Training of GYN care team on HIV, PrEP indication, PrEP care (for both daily and long-acting injectable regimens), and stigma 3. PrEP indication job aids 4. Electronic medical record documentation aids, including pre-templated notes and order sets	5. Educational materials for Black cis-gender women on HIV and PrEP 6. Asynchronous training on effective communication strategies with patients about sexual health and PrEP				
Implementation Strategy	Number 1	Number 2	Number 3	Number 4	Number 5	Number 6
Actor	Medical assistant or care provider	Study staff/ PrEP expert	PrEP expert	PrEP expert and information technician	PrEP expert and graphic designer	PrEP expert
Action	Charts evidence based sexual history questionnaire in the medical record 	Provides 1.5 hour training on HIV, risk, and PrEP indications and care	Creates easily accessible pocket cards with indications for PrEP 	Creates templates in electronic medical record for PrEP visits and order sets	Develops informational content to include in educational materials tailored to Black cis-gender women	Develops 15-30 minute training tutorial on how to communicate with patients about sexual health and PrEP, tailored to Black cis-gender women
Target	Patient	Providers/staff	Provider	Provider	Patient	Patient
Temporality	Medical assistant – Before every patient encounter with a provider OR Provider – Beginning of every visit	1-month prior to PrEP4Her being implemented at our pilot site	Continuously carried by providers and displayed in shared workspaces	1-month prior to PrEP4Her being implemented with instructions on how to access placed in shared workspaces and sent through email communications	Placed in waiting areas and/or private exam rooms, accessible during every visit and replenished by study staff	1-month prior to PrEP4Her being implemented and presentation accessible in shared work space as well as emailed to all providers

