Dose	5-minute screener at every visit	1.5 hour training occurring once prior to 6-month pilot	As needed by providers during clinical care	As needed by providers during charting	Available during the entire 6-month pilot for every clinic	Once prior to 6-month pilot and then available as needed
Implementation Outcomes affected	Please see Figure 2. for detailed description of how each implementation strategy maps to implementation outcomes. In short, we will be evaluating the following proximal implementation outcomes: reach, adoption, fidelity, acceptability, and preliminary effectiveness. Distal outcomes will not be evaluated in this study.					
Justification	Implementation strategy components selected for this study have been selected based on observed, researched or hypothesized barriers based on review of the literature. These components may be subject to change based on findings in Aim 1 and feedback from our CAB.					

**Pilot intervention development with CAB:** We will engage members of our CAB, including key stakeholders in GYN clinic operations, care and management as well as Black cis-gender women (aged between 18-45) bi-weekly over a 3-month period of time (see structure above). During this time, we will conduct IM (outlined above) and pilot materials developed as a part of selected implementation strategy components. After implementation strategy materials have been refined, we will review appropriate operational steps needed to integrate PrEP into our clinical site. For implementation strategy selection and content development, we will work closely with [name] who has expertise in implementation science working with family planning clinics in Southern settings to improve HIV prevention among Black cis-gender women. We will meet with [name] monthly, in one-hour meetings with a consultation fee of \$100/hour. (See Letter of Support)

**Specific Aim 3. Pilot PrEP4Her, refined through Aim 2, to deliver PrEP for Black cis-gender women attending routine gynecologic care visits.**

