### Objectives

(Primary manuscript) Mixed methods paper evaluates the implementation outcomes, using the RE-AIM framework, of the PrEP4Her intervention in a low barrier gynecology setting.

(Primary/Fidelity) Described fidelity to PrEP4Her from the end-user perspective. Describe results from survey, compare/contrast with EHR review (EHR data confirms the number of PrEP prescriptions)

**Study population:** Reproductive aged women 18-45 who received the PrEP4Her intervention as a component of their standard care from January 2023 – August 2024 [Pre-implementation stage Jan – July 2023; PrEP4Her implementation July 2023 January 2024; Pilot January 2024-August 2024].

**PreP4HER components** - Universal sexual history screener, synchronous PrEP training, job aides [pocket cards with CDC PrEP guidance and 5Ps, EHR documentation/order aids, educational materials, asynchronous training on communication strategies

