#### Quantitative data

1. Visits per period (of intervention) with number of PrEP prescriptions
  - a. Patient visits by intervention period; total n=4161
  - b. PrEP prescriptions per period; n=11
2. EHR review (to confirm PrEP prescriptions)
  - a. Total charts reviewed n= 4635; missing =6
3. Demographics of all patients
  - a. Race
  - b. Sex at birth assignment
  - c. Gender in EHR
  - d. Lab results
    - i. Chlamydia
    - ii. Gonorrhea

- iii. Syphilis
- iv. HIV

4. Demographics of patients with a PrEP prescription

- a. Race
- b. Sex assigned at birth
- c. Gender assigned in HER
- d. Lab results
  - i. Chlamydia
  - ii. Gonorrhea
  - iii. Syphilis
  - iv. HIV

5. Sexual health pre-screener survey; n=1135

- a. Sociodemographics
  - i. Race
  - ii. Sex assigned at birth
  - iii. Gender in EHR
  - iv. Lab results
    - 1. Chlamydia
    - 2. Gonorrhea
    - 3. Syphilis
    - 4. HIV
- b. Sexual health pre-screener outcomes; n=1135
  - i. Types of sexual behaviors
  - ii. Gender of partners
  - iii. Sexually active in last year
  - iv. Number of sexual partners in past year
- c. Data on when participants were seen (by month/year)

6. Post visit (fidelity) survey data; n=242

- a. Demographics
  - i. Race
  - ii. Education
  - iii. Employment
  - iv. Insurance
  - v. Estimated household income
  - vi. Reason for visit
  - vii. Anal sex in past 6 months
  - viii. Condom use history
  - ix. Number of partners
  - x. Gonorrhea or syphilis diagnosis, past 6 months
  - xi. Partner living with HIV and not on medication
  - xii. Did provider take sexual history?

- xiii. Saw educational materials during visit?
- xiv. Spoke with provider about PrEP?
- xv. Prescribed PrEP during visit?

- b. Fidelity items
  - i. Comfort discussing PrEP w/ provider
  - ii. Understood side effects of PrEP after discussion w/ provider
  - iii. Provider discussed how to pay for PrEP
  - iv. Felt confident could take PrEP daily after visit
- c. Row percentages -Talked to doctor about PrEP and demographics

7. PrEP prescriptions data with physician and intervention period

- a. Demographics of patient prescribed; n=11
  - i. Race
  - ii. Age
  - iii. Lab results
  - iv. Earliest Emtricitabine-Tenofovir
  - v. Study Prescription Date
  - vi. Order Date

8. Number of women with a PrEP indication seen during the study visit (no indication/STI in last 12 months/multiple partners/STI in last 12 months and multiple partners); n=4241

- a. Data by visit date

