**Procedures:**

- a. **Frequencies of PrEP prescriptions by**
- b. **Report demographics of patients prescribes PrEP**
- 3. **Adoption:** Defined as the proportion of key-stakeholders within our pilot site who were willing to initiate our implementation strategy.

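### An investigator practises in the pilot clinic as an embedded champion, a role outside the six listed components, and no planned output shows prescribing, adoption or feasibility apart from the study team

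*Combined protocol and SAP*

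**What the plan says.** Protocol section C4, item (1), expects that busy clinical teams may be slow to take up PrEP4Her, and that poor adoption and fidelity would weaken its results. It gives two remedies. In the first, "investigators will work with leadership in identifying “champions” within the clinic setting to encourage PrEP4Her implementation". The second is already in place: "Inclusion of a physician practicing in the GYN continuity clinic as a part of our investigative team embeds a committed champion within our pilot site".

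The strategy being piloted is defined by six components. Protocol Table 4 numbers them, ending with "Asynchronous training on effective communication strategies with patients about sexual health and PrEP", and Figure 3 repeats them. Table 4 allows revision: "These components may be subject to change based on findings in Aim 1 and feedback from our CAB". The SAP, started in September 2025 after the pilot had ended, gives the same six, beginning "Universal sexual history screener, synchronous PrEP training, job aides". No list includes a champion.

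The outcomes at issue are defined as follows.

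- **Reach** (protocol Aim 3; SAP Paper 1) is a raw count of Black cis-gender women given a PrEP prescription.
- **Preliminary Effectiveness** is a rise in prescriptions over time, against a stated baseline of none. In the SAP, the first output under this outcome stops before naming the variable by which frequencies will be broken down.
- **Adoption** is "Defined as the proportion of key-stakeholders within our pilot site who were willing to initiate our implementation strategy". It is measured through training attendance, website clicks, a one-item survey and a chart review of sexual histories.
- **Feasibility** rests on FIM ratings by key stakeholders, summarised together. Its purpose is stated: "We will measure whether PrEP4Her is appropriate for a larger, full-scale implementation trial".

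SAP item 7 under Quantitative data is titled "PrEP prescriptions data with physician and intervention period". Its sub-items are race, age, laboratory results and prescription or order dates.

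**The concern.** The champion is there to move the outcomes that the pilot measures. Someone who is both investigator and clinic physician could contribute as a prescriber, a training attendee and a rater of feasibility. As the plan stands, that contribution would be merged with that of routine staff.

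This bears on the next step. Section C6 makes feasibility, acceptability and preliminary efficacy the condition for seeking a fully powered multi-site trial. The documents do not say whether the later sites would have an investigator on staff. A finding that six components were enough, and a finding that six components plus an embedded investigator were enough, would support different trials. The planned outputs cannot tell the two apart.

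There is also a reporting gap. In Aim 2 the protocol undertakes to specify each component by actor, action, target, timing, dose, outcome affected and justification. The champion role has no such specification, so another site could not tell what was done.

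**Working it through.** No stated sample size or power figure bears on this point, so there is none to reproduce. The check has two parts: what each output separates, and how far one person could move it.

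**1. What is separated**

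| Outcome | Information held | Rule or output that separates study-team members |
|---|---|---|
| Reach, Effectiveness | Prescriptions with physician (SAP item 7) | None specified, though the data allow it |
| Adoption | Attendance, clicks, one-item survey | None |
| Feasibility (FIM) | Stakeholder ratings, pooled | None |
| Acceptability | 7 key informant and 18 participant interviews (SAP) | None |

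**2. Prescriptions**

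Inputs: 11 prescriptions (SAP, Quantitative data, items 1 and 7). Eleven is also the ceiling for Reach, which counts Black women only. The investigator's share, k, is not given, so the whole range from 0 to 11 is open.

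Other clinicians' count: x = 11 − k. Exact Poisson 95% limits: lower = χ²(0.025; 2x)/2, upper = χ²(0.975; 2x + 2)/2, with lower limit 0 when x = 0.

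| k (assumed) | Investigator's share, k/11 | Others, x | 95% limits for x |
|---|---|---|---|
| 0 | 0% | 11 | 5.5 to 19.7 |
| 3 | 27% | 8 | 3.5 to 15.8 |
| 6 | 55% | 5 | 1.6 to 11.7 |
| 10 | 91% | 1 | 0.0 to 5.6 |
| 11 | 100% | 0 | 0 to 3.7 |

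At k = 0 nothing changes. At k = 10 or 11 there is almost no evidence of prescribing by routine staff. I give counts and not rates because the SAP lists visits by period (4161 in all) but not by physician.

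**3. Ratings**

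The SAP does not give the number of FIM raters. The weight of one rater is 1/n:

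- the 7 key informants: 1/7 = 14.3%
- the roughly 10 providers, managers and support staff planned in the protocol: 1/10 = 10%
- all 7 + 18 = 25 interviewees: 1/25 = 4%

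The protocol summarises FIM by median and interquartile range, so the effect depends on the other ratings. With six hypothetical ratings of 3, 3, 3, 4, 4, 4, adding one 5 moves the median from 3.5 to 4. With 3, 3, 3, 3, 4, 4, it stays at 3.

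**4. Adoption**

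No denominator is given, so no size can be calculated.

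**The case against.** The strongest reply is that the harm is conjectural. Nothing says that this physician prescribed PrEP, was counted in training, was one of the 7 key informants or completed the FIM, and k = 0 fits the text as well as any other value. The physician already practised in the clinic and was not brought in from outside. Champions are disclosed in C4, and other sites could identify their own. The study is a one-arm descriptive pilot that the protocol itself expects to need further refinement, and it does not attribute prescriptions to single components. All of this stands, and it is why the point concerns reporting and not a demonstrated bias.

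A reader might infer that the investigator's prescriptions cannot be told apart. The documents do not support that: item 7 links prescriptions to physicians. What is missing is an output that uses the link.

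A reader might also conclude that this physician should be excluded, or that the champion must be counted as a seventh component. Neither follows. Adoption is defined over stakeholders at the pilot site, and a physician practising there is one of them. Whether a champion is a component, a precondition or context is open to argument. The logic model is said to cover moderators and preconditions, and the copy reviewed lacked Figure 2 and the text between sections B3 and C2, so a mention there cannot be ruled out.

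Finally, splitting by prescriber does not remove the champion's influence, because champions are meant to encourage colleagues. That is correct, and it limits what the split can show.

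**Conclusion.** The point holds as a gap in planned reporting. The plan describes an investigator embedded in the clinic as champion, lists no champion among the components, and specifies no output that shows Reach, Effectiveness, Adoption or FIM apart from the study team.

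The size is unknown. Depending on the investigator's share, prescriptions by other clinicians could be anywhere from 0 to 11. One rater would carry between 4% and 14% of the FIM sample, depending on who completed it. These ranges assume that the SAP's 11 prescriptions and its interview counts are the analysed numbers. They illustrate what one person could do and are not estimates of what happened.

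A reader might infer that the investigator produced the increase from zero, or that adoption and feasibility are inflated by construction. The documents support neither. Each would require this physician to have been counted, and that is not stated.

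The change is worth making: the results feed a decision about other sites, the counts are small, and the prescriber is already recorded.

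**What to change.** In Paper 1 of the SAP:

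1. Complete the unfinished prescription-frequency output under Preliminary Effectiveness. Give counts for the investigator-physician versus other clinicians, and the number of distinct prescribers, using item 7. Give the same split for Reach.
2. Flag study-team members in the training, FIM and key-informant data. Report Adoption, FIM and key-informant results with and without them. If none was counted, one sentence saying so is enough.
3. State that all figures, including those for non-investigators, were obtained at a site with an embedded investigator champion. Describe what the champion did, and limit the conclusion about other sites accordingly.

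The cost is SAP wording, one split of data already held and a simple flag on the staff records. The downside is that the figures credited to routine staff may be lower and the split counts will be very small, so they should be presented as description without tests.
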